## **Introduction**

Adult and juvenile dermatomyositis (DM) are systemic immune-mediated inflammatory diseases most commonly affecting the skin and musculoskeletal system. Amyopathic dermatomyositis is a subtype of dermatomyositis that affects only the skin and lacks the characteristic muscle involvement. Treatment of these conditions, in particular the cutaneous manifestations, is challenging and currently no universally effective single treatment exists. Many patients have cutaneous manifestations that are refractory to numerous medications (1, 2).

## **Background and Significance**

H.P. Acthar gel (adrenocorticotropic hormone gel) received FDA approval for treatment of a variety of diseases, including dermatomyositis, in 1952. Despite this there is a paucity of clinical data concerning the efficacy of H.P. Acthar gel for treating dermatomyositis. Recently a small, retrospective case series describing significant improvement in both cutaneous and musculoskeletal symptoms in 5 patients with refractory dermatomyositis treated with H.P. Acthar gel was reported and has resulted in renewed interest in use of this medication in dermatomyositis patients (3). The proposed efficacy of H.P. Acthar gel has been attributed to its unique ability to induce production of endogenous cortisol, corticosterone, aldosterone, and to bind melanocortin receptors on lymphocytes and other cells to modulate immunologic responses. Our hypothesis is that H.P. Acthar gel will be safe and effective for treating the cutaneous manifestations of dermatomyositis in patients with refractory classic dermatomyositis, juvenile dermatomyositis, and amyopathic dermatomyositis.

## **Study Design**

### **Methods**

Prospective, Open-label study

### **Sample**

Our sample will include approximately 10-15 patients with refractory cutaneous symptoms related to either classic dermatomyositis, juvenile dermatomyositis, or amyopathic dermatomyositis. This sample size was chosen to ensure adequate power to detect 50% decreases in the mean total and activity scores of the modified CDASI, and 75% decreases in the mean damage scores. This is not affected by the baseline modified CDASI score (though the % change and coefficient of variation will change based on this level).

Our inclusion/exclusion criteria are as follows:

***Inclusion Criteria:***

- Patients  $\geq$  18 years old with refractory cutaneous symptoms related to either classic dermatomyositis (CD), juvenile dermatomyositis (JD), or amyopathic dermatomyositis(AD). Diagnosis will be based on either Bohan and Peter criteria (CD and JD) or Sontheimer's criteria (AD) (4-7).
- Patients must have had a skin biopsy with histologic features consistent with dermatomyositis and current cutaneous manifestations consistent with dermatomyositis.
- Although not mandatory, patients with evidence of current or previous active myositis will be eligible for enrollment. Patients will be considered to have refractory disease if cutaneous manifestations exist despite treatment with steroids at least one steroid-sparing systemic treatment commonly found to be useful in patients with dermatomyositis. These may include azathioprine, cyclosporine, mycophenolate mofetil, IVIG, methotrexate, cyclophosphamide, chlorambucil, sirolimus, adalimumab, infliximab and rituximab.
- Use of topical medications and sunscreen currently and in past will be noted but not weighed for assessment of refractory cutaneous disease.

***Exclusion criteria:***

- Patients with dermatomyositis who have minimal-to-no active cutaneous features (focal involvement with less than 1% total body surface area involved).

- Patients whose cutaneous findings are not consistent with dermatomyositis and/or have previous biopsy results suggestive of an alternative diagnosis
- Patients with inflammatory myositis other than dermatomyositis, such as polymyositis or inclusion body myositis.
- Patients with malignancy-associated dermatomyositis
- Patients with clear features of an overlap myositis
- Patients younger than 18 years old
- Patients with acutely active or chronic infections.
- Patients with uncontrolled diabetes, hypertension, cardiovascular, hepatic, or renal disease
- Pregnant or lactating females.
- Patients with any medical condition that is felt by the primary investigator to place the patient at unreasonable risk for adverse effects during treatment with H.P. Acthar.
- Hypersensitivity to H.P. Acthar, any of its components (allergy to pig-derived proteins)
- Patients with osteoporosis
- Patients who have had surgery within 8 weeks of screening
- Patients with a history of or current gastric ulcers
- Patients taking daily doses of systemic corticosteroids greater than the equivalent of 40mg prednisone.

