## **Research Procedures**

- 1) Upon enrollment patients will undergo a thorough history (including assessing time of diagnosis), review of systems, and a complete physical examination.
- 2) A detailed examination of the skin and mucous membranes will be performed, noting for presence/absence of the following: scalp erythema and atrophy, heliotrope rash, typical erythema and atrophy of sun-exposed areas on the neck, upper chest and upper back (shawl sign), erythema +/- scaling of the elbows and/or knees (Gottron's sign), gottron's papules, periungual erythema, ragged cuticles, proximal nailfold capillary loops, palmar scaling and hyperkeratosis (mechanic's hands), a rash involving the hips (holster sign), oral ulcerations, cutaneous ulcerations, purpura.
- 3) Objective cutaneous dermatomyositis scoring by the primary investigator using the **modified Cutaneous Dermatomyositis Disease Area and Severity Index** (CDASI) score and **Abbreviated Cutaneous Assessment Tool** (aCAT) will be performed at each visit ([8-13](#)).
- 4) Objective general cutaneous disease scoring by the primary investigator using the **Physician Global Activity** for (a) **overall skin** (b) **skin activity** (c) **skin damage** will be performed at each visit (each assessed using both VAS-0-10 visual analog scale and Likert scale- 0-4 for each) ([9](#)).
- 5) Objective scoring tools to be completed by the patient at each visit will include: **Patient Global Assessment (Skin) Score** (0-10 visual analog scale), **Patient Global (Itch) Score** (0-10 visual analog scale), and the **Dermatology Life Quality Index** (validated quality of life assessment) ([8-12](#)).
- 6) Photographs of all cutaneous lesions will be performed at baseline and at each follow-up visit.
- 7) Evaluation for current presence of myositis will be performed using the **Manual Muscle Testing 8 (MMT-8)** scoring tool by the primary investigator, as well as with serologic studies below ([11, 12](#)).
- 8) Completion of the **Myositis Disease Activity Assessment Tool** (MDAAT) by the primary investigator to assess disease activity of extramuscular organ systems ([12](#)).
- 9) Serologic studies at baseline will include an AM cortisol level, CBC w/ diff, CMP, CK, aldolase, LDH, comprehensive myositis panel (ARUP labs), C3, C4, and HbA1c. The above serologic studies (except for the comprehensive myositis panel) will be repeated at the final visit.

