10) Patients may continue their current immunosuppressive treatment regimens at the time of starting H.P. Acthar. If it is felt that patients should taper off of medications they will require a washout period:

- corticosteroids- 2 weeks
- methotrexate/azathioprine/mycophenolate/cyclosporine/sirolimus- 4 weeks
- adalimumab/infliximab/IVIG/chlorambucil/cyclophosphamide- 8 weeks
- rituximab- 6 months.

They will be instructed to continue topical medications, moisturizers, and sunscreen based on their current practice, which will be recorded at baseline and during subsequent visits.

11) All patients will receive 80 U (1 mL) of H.P. Acthar gel via subcutaneous injection twice weekly for 24 weeks (approximately 6 months).

12) Patients will require **follow-up visits in person at 1mo (+/- 5 days), 3mo (+/- 5 days), and 6mo (+/- 5 days)** after initiation of the H.P. Acthar, at which time examinations and clinical scoring tool assessments will be repeated.

13) If corticosteroids are continued in patients receiving H.P. Acthar gel they will be tapered at the primary investigator's discretion based on clinical evaluation at follow-up appointments.

14) H.P. Acthar will be discontinued in any given patient at the primary investigator's discretion if deemed necessary for the patient's overall health and well-being at any point during the study.

Serologic Studies	Baseline	6mo
CBC w/ diff	X	X
CMP	X	X
AM cortisol level	X	X
Creatine Kinase	X	X
Aldolase	X	X
LDH	X	X
C3	X	X
C4	X	X
HbA1c	X	X
Comprehensive myositis panel (ARUP labs)	X	

Length of above tests is that of a typical phlebotomy blood draw.

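### Pregnancy is an exclusion, but no listed procedure, laboratory test or schedule row includes a pregnancy test, so an early unrecognised pregnancy could be dosed

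*Combined protocol and SAP*

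**What the plan says.** The Exclusion criteria rule out "Pregnant or lactating females". The Inclusion Criteria admit patients aged 18 or older and set no limit by sex or childbearing potential, so the exclusion has to be applied to real candidates.

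Three places in the protocol describe what is done at baseline:

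- Research Procedures, item 1: "Upon enrollment patients will undergo a thorough history (including assessing time of diagnosis), review of systems, and a complete physical examination". Pregnancy, menstrual history and contraception are not mentioned.
- Research Procedures, item 9: "Serologic studies at baseline will include an AM cortisol level, CBC w/ diff, CMP, CK, aldolase, LDH". Four further tests complete the list, which ends with HbA1c. The serology table that follows item 14 repeats this list.
- The clinical assessment table under Research Protocol Guidelines (continued), which holds physician-scored and patient-scored tools only.

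Two further items bear on timing. Under item 10, patients may stay on their current immunosuppressive treatment. Only otherwise does a washout apply: "If it is felt that patients should taper off of medications they will require a washout period". Under item 11, all patients then receive the "gel via subcutaneous injection twice weekly for 24 weeks".

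**The concern.** An exclusion protects patients only if someone can establish that it applies. History and examination depend largely on what the patient knows or what can be seen, and an early pregnancy may be neither known nor visible. Staff who followed the procedure list and both tables exactly as written would order no pregnancy test. They could then give the drug to a patient whom the plan means to keep out. What is at stake is the safety of that patient and the pregnancy, not the trial's results.

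**Working it through.** The plan gives no figure of its own on this point, so the check is a count and a comparison of sections.

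1. **Baseline tests in the text (item 9).** AM cortisol, CBC with differential, CMP, CK, aldolase, LDH, myositis panel, C3, C4, HbA1c: 10 tests, of which 0 are pregnancy tests.
2. **Baseline rows in the serology table.** CBC with differential, CMP, AM cortisol, creatine kinase, aldolase, LDH, C3, C4, HbA1c, myositis panel: 10 rows, the same 10 tests, of which 0 are pregnancy tests.
3. **Clinical assessment table.** Modified CDASI, aCAT, PGA by VAS, PGA by Likert, patient global, patient itch, DLQI, MMT-8, MDAAT: 9 rows, all scoring tools.
4. **Elsewhere.** The surviving text has no urine test, no definition of childbearing potential and no check of pregnancy status before the first dose. The Consent section names no test either.
5. **What remains.** Item 1 is the only listed enrolment procedure that could bring a pregnancy to light. The protocol does not tie it to this exclusion; that it serves the exclusion is a fair inference. It can pick up a known pregnancy, and lactation. It cannot be relied on for an early pregnancy that the patient does not know of.
6. **Later safeguards.** Item 14 provides that "H.P. Acthar will be discontinued in any given patient" at the investigator's discretion, and patients are told to call with adverse events. Both help only once somebody suspects a pregnancy.

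Steps 1 to 4 show that the supplied procedures contain no test. Steps 5 and 6 narrow the gap to one case: a pregnancy present but unrecognised at the first injection.

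**The case against.** The strongest reply is that absence from these lists is weak evidence.

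- **The lists are not expressly exhaustive.** Item 9 is worded as what the studies will include, and it and its table are headed as serology, where a urine test would not belong. The Exclusion criteria mention screening, yet no screening procedures are described. Some pages were removed before review. All of this stands, so the finding is limited to the supplied text. Against it, the procedure list and both tables are present and agree with one another, and they are where staff would look for such a test.
- **Other exclusions also lack a stated method.** Osteoporosis, gastric ulcers and chronic infection are left to history, examination and judgement too. This is the style of a short protocol, and the observation is fair. Pregnancy still merits its own line, because its status can change between enrolment and the first dose and one inexpensive test settles it.
- **The enrolment assessment already covers pregnancy.** It does for known pregnancy and for lactation, and the finding does not dispute that.

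Two stronger readings are tempting but not supported:

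- A reader might count the injections due before the 1-month visit and present them as the size of the harm. Item 12 times visits "after initiation of the H.P. Acthar, at which time examinations and clinical scoring tool assessments will be repeated". Nothing makes that visit a point at which pregnancy would be found, so the count measures neither time to detection nor harm.
- A reader might infer from the longest washout, 6 months for rituximab, that a patient's status could be that old at the first injection. Washout is optional, and the text does not say whether baseline comes before or after it. Because the primary endpoint compares end of study with baseline and visits run from the start of treatment, a baseline taken long before dosing is the less natural reading. The washout provision supports a conditional repeat test and nothing more.

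**Conclusion.** The concern holds in a limited form. The supplied procedures, laboratory lists and schedules include no pregnancy test, and the general assessment at enrolment may miss an early unrecognised pregnancy, so a patient whom the plan intends to exclude could be dosed.

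This is a minor safety improvement. Its size cannot be stated as an expected number or as a level of harm: the plan enrols about 10 to 15 adults and gives neither the proportion who could be pregnant nor any fetal-risk data. Endpoints, sample size and analysis are unaffected.

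The conclusion assumes that no test is specified in the removed pages and that staff follow the lists as written. It covers pregnancy present at the first dose, not conception during treatment. A reader might infer that the plan has no means at all of applying the exclusion; the documents do not support that, since item 1 can identify a known pregnancy.

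**What to change.** Add to Research Procedures, item 9, and to the serology table, a pregnancy test for patients who could be pregnant: serum hCG on the existing baseline draw, or a urine test. Require a negative result shortly before the first injection, for example within 7 days. If an optional washout makes the baseline result older than that, repeat with a urine test before the first dose. Keep the item 1 assessment for known pregnancy and lactation.

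The cost is one line of text, one table row, one low-cost test per such patient (a second where washout requires it) and a short wait for the result.

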## **Research Procedures**

- 1) Upon enrollment patients will undergo a thorough history (including assessing time of diagnosis), review of systems, and a complete physical examination.
- 2) A detailed examination of the skin and mucous membranes will be performed, noting for presence/absence of the following: scalp erythema and atrophy, heliotrope rash, typical erythema and atrophy of sun-exposed areas on the neck, upper chest and upper back (shawl sign), erythema +/- scaling of the elbows and/or knees (Gottron's sign), gottron's papules, periungual erythema, ragged cuticles, proximal nailfold capillary loops, palmar scaling and hyperkeratosis (mechanic's hands), a rash involving the hips (holster sign), oral ulcerations, cutaneous ulcerations, purpura.
- 3) Objective cutaneous dermatomyositis scoring by the primary investigator using the **modified Cutaneous Dermatomyositis Disease Area and Severity Index** (CDASI) score and **Abbreviated Cutaneous Assessment Tool** (aCAT) will be performed at each visit ([8-13](#)).
- 4) Objective general cutaneous disease scoring by the primary investigator using the **Physician Global Activity** for (a) **overall skin** (b) **skin activity** (c) **skin damage** will be performed at each visit (each assessed using both VAS-0-10 visual analog scale and Likert scale- 0-4 for each) ([9](#)).
- 5) Objective scoring tools to be completed by the patient at each visit will include: **Patient Global Assessment (Skin) Score** (0-10 visual analog scale), **Patient Global (Itch) Score** (0-10 visual analog scale), and the **Dermatology Life Quality Index** (validated quality of life assessment) ([8-12](#)).
- 6) Photographs of all cutaneous lesions will be performed at baseline and at each follow-up visit.
- 7) Evaluation for current presence of myositis will be performed using the **Manual Muscle Testing 8 (MMT-8)** scoring tool by the primary investigator, as well as with serologic studies below ([11, 12](#)).
- 8) Completion of the **Myositis Disease Activity Assessment Tool** (MDAAT) by the primary investigator to assess disease activity of extramuscular organ systems ([12](#)).
- 9) Serologic studies at baseline will include an AM cortisol level, CBC w/ diff, CMP, CK, aldolase, LDH, comprehensive myositis panel (ARUP labs), C3, C4, and HbA1c. The above serologic studies (except for the comprehensive myositis panel) will be repeated at the final visit.

10) Patients may continue their current immunosuppressive treatment regimens at the time of starting H.P. Acthar. If it is felt that patients should taper off of medications they will require a washout period:

- corticosteroids- 2 weeks
- methotrexate/azathioprine/mycophenolate/cyclosporine/sirolimus- 4 weeks
- adalimumab/infliximab/IVIG/chlorambucil/cyclophosphamide- 8 weeks
- rituximab- 6 months.

They will be instructed to continue topical medications, moisturizers, and sunscreen based on their current practice, which will be recorded at baseline and during subsequent visits.

11) All patients will receive 80 U (1 mL) of H.P. Acthar gel via subcutaneous injection twice weekly for 24 weeks (approximately 6 months).

12) Patients will require **follow-up visits in person at 1mo (+/- 5 days), 3mo (+/- 5 days), and 6mo (+/- 5 days)** after initiation of the H.P. Acthar, at which time examinations and clinical scoring tool assessments will be repeated.

13) If corticosteroids are continued in patients receiving H.P. Acthar gel they will be tapered at the primary investigator's discretion based on clinical evaluation at follow-up appointments.

14) H.P. Acthar will be discontinued in any given patient at the primary investigator's discretion if deemed necessary for the patient's overall health and well-being at any point during the study.

Serologic Studies	Baseline	6mo
CBC w/ diff	X	X
CMP	X	X
AM cortisol level	X	X
Creatine Kinase	X	X
Aldolase	X	X
LDH	X	X
C3	X	X
C4	X	X
HbA1c	X	X
Comprehensive myositis panel (ARUP labs)	X	

Length of above tests is that of a typical phlebotomy blood draw.

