## **Adverse Events and Data Monitoring Committee(DMC)**

- Patients will be instructed to call immediately with any adverse events. All adverse events will be recorded during the administration of H.P. Acthar. Any serious adverse events will be reported immediately to the appropriate contact person at Questcor, as well as to the IRB in accordance with their policy.
- A DMC will not be used because H.P. Acthar is an approved drug for treatment of dermatomyositis.

- A DRC is not planned given that Acthar is currently used in clinical medicine to treat multiple sclerosis and has a well-known adverse effect profile with low risk of significant adverse events.
- An interim analysis is not planned.

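### No blood draw is tied to an early stop of study drug, and adverse effects are not asked about at follow-up visits, so end-points 2f and 2c may misstate what happened on drug

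*Combined protocol and SAP*

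**What the plan says.** All references are to the combined protocol and SAP.

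- **Bloods.** Research Procedures item 9 sets a baseline panel in which CMP, AM cortisol and HbA1c are included. On the repeat draw it states: "The above serologic studies (except for the comprehensive myositis panel) will be repeated at the final visit". The table that follows item 14 is headed "Serologic Studies Baseline 6mo" and has no other time column.
- **Visits.** Item 12 requires patients to attend at 1, 3 and 6 months after the drug is started, each within 5 days, "at which time examinations and clinical scoring tool assessments will be repeated". The Clinical Assessments table lists nine scores at those visits and no laboratory row. Item 1 places the history, the review of systems and the physical examination at enrollment.
- **Stopping.** Item 14 allows the investigator to stop the drug "if deemed necessary for the patient's overall health and well-being at any point during the study". No early-stop visit or early-stop panel is described.
- **Adverse effects.** The section on adverse events says "Patients will be instructed to call immediately with any adverse events" and that adverse events during dosing will be recorded. It describes no other way of eliciting them.
- **End-points.** Secondary end-point 2c is safety and tolerability, judged by how often adverse effects occur and of what kind. Secondary end-point 2f is the change in HbA1c.

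**The concern.** The Background says the drug can "induce production of endogenous cortisol, corticosterone, aldosterone", and the exclusion list names "Patients with uncontrolled diabetes, hypertension, cardiovascular, hepatic, or renal disease". Safety is part of the study hypothesis, and HbA1c is an end-point in its own right. The two secondary end-points that carry the safety message therefore need data that belong to the period on drug, collected in the same way for every patient.

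Two gaps stand in the way. First, a patient who stops early may contribute an HbA1c taken months after the last injection, or no second value at all. A baseline-to-end change that pools such values with those of patients who completed the course does not describe one exposure. Second, if patients must volunteer their adverse effects by telephone, the count behind 2c depends on how readily each patient calls. The study has no control group, so there is no comparison arm in which the same under-reporting would occur.

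**Working it through.** There is no stated figure to reproduce on this point. The check compares the schedules and computes the intervals they imply. The baseline draw is assumed to fall on day 0.

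**1. Draws during dosing.** Item 11 gives injections twice weekly for 24 weeks: 24 × 7 = 168 days and 24 × 2 = 48 scheduled injections. Item 9, item 12 and both tables agree that no draw is scheduled between baseline and the last one.

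**2. Length of the gap.** Item 11 treats 24 weeks as roughly 6 months, so two readings are open:

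- 6 months as 24 weeks: 6 × 28 = 168 days, within 5 days either way.
- 6 calendar months: 6 × 365.25/12 = 182.6, about 183 days, within 5 days either way.

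On the calendar reading the last draw falls 182.6 − 168 = 14.6, about 15 days after week 24. With the window this is 9.6 to 19.6, about 10 to 20 days. Even a patient who completes the course would then have no scheduled blood during dosing.

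**3. What happens after an early stop.** Item 9 ties the repeat panel to the final visit; the table ties it to 6 months. Item 12 counts visits from the start of drug and does not change them for a patient who stops.

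- *Stops drug and keeps attending.* The final visit is the month-6 visit, so both wordings give the same draw. A stop at month 1 leaves 6 − 1 = 5 months off drug; a stop at month 3 leaves 6 − 3 = 3 months.
- *Stops drug and leaves the study at a visit.* Under item 9 the panel could be drawn at that visit, if it is recognised as the last. Under the table there is no second panel.
- *Stops between visits and does not return.* Neither wording yields a second panel.

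**4. Weight in end-point 2f.** The documents give no discontinuation rate. As an illustration, assume one or two early stoppers among the planned 10 to 15 patients:

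- one of 15: 1/15 = 7%; one of 10: 1/10 = 10%
- two of 15: 2/15 = 13%; two of 10: 2/10 = 20%

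**5. Capture of adverse effects.** Item 1 names history, review of systems and physical examination as separate things. Item 12 carries forward examinations and scoring tools only. None of the nine listed scores is described as a record of adverse effects. The patient's call is therefore the only route the document states.

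**The case against.** The schedule for bloods is internally consistent: item 9, the serology table and item 12 all put them at the start and the end only. The protocol also gives reasons for light monitoring. It describes an approved drug with a known adverse-effect profile and low risk, and it excludes uncontrolled disease and anyone the investigator judges to be at unreasonable risk. Patients are examined in person three times, all adverse events during dosing are to be recorded, and unscheduled tests are not forbidden. Item 9's final visit can be read as the last visit attended, which would already cover some early stoppers.

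Much of this stands, and it rules out several stronger readings that a reader might infer:

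- *That laboratory changes go unseen.* A change that persists to the last draw would be seen, and symptomatic events can be phoned in. The documents support only that no draw is scheduled in between.
- *That 2c and 2f understate harm.* This is not shown. For 2f, any bias needs early stoppers, and its direction depends on why they stopped. Corticosteroid tapering under item 13 could also move HbA1c. For 2c, under-counting is possible but not demonstrated.
- *That the gap is 26 weeks and exceeds the dosing period.* This holds only if 6 months means calendar months.
- *That the plan is wrong not to draw chemistry and HbA1c at 1 and 3 months.* The passages do not contradict one another on this, and no figure in them fixes an interval. It is a clinical monitoring decision.

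What the objection does not answer is the early-stop case. A known drug profile says nothing about when HbA1c should be measured for 2f, and the final-visit reading does not help a patient who stops drug but keeps attending. Nor does an examination ensure that each patient is asked about adverse effects.

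**Conclusion.** The point holds in a limited form. Bloods are scheduled twice, 168 to about 183 days apart, across all 48 planned injections, and no draw is linked to an early stop. On the month-6 reading, the next HbA1c for a patient who stops at 1 or 3 months is about 5 or 3 months off drug, or missing. End-point 2f may therefore not reflect exposure in early stoppers. The 7% to 20% share rests on an assumed one or two stoppers, since the plan states no number. End-point 2c may be under-counted because the only stated route is the patient's call; the size of any under-count cannot be estimated from the documents. The primary end-points and the sample size are not affected. These are inexpensive improvements to two secondary end-points.

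**What to change.** 1. Reconcile the final visit in item 9 with the 6-month column in the serology table, and say whether 6 months means 24 weeks or calendar months. State that the already planned final panel is taken when study drug is stopped early. Report end-point 2f with on-drug and off-drug values identified, and give the number of patients without a second value.
2. In item 12, repeat the item 1 review of systems and record adverse effects at the existing 1-, 3- and 6-month visits, in addition to patient calls.

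The cost is a few minutes per visit, possibly one unscheduled draw for a patient who stops early, and short edits to items 9 and 12 and the table. No extra visit is needed for patients who complete the course. Whether to add chemistry or HbA1c at the 1- and 3-month visits is for the sponsor and investigator to decide; no schedule is proposed here. Decisions on continuing or stopping drug remain as item 14 has them.
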